7.4 VARIABLES

7.4.1 **Exposures**

The exposure measures are based on pharmacy dispensings of the study medications, namely Tio+Olo and LABA/LAMA/ICS combination therapy. As described in the data analysis section, the as-treated analysis, which is the main analysis, will consider continuing exposure of the initial treatment of Tio+Olo or LABA/LAMA/ICS within the treated groups defined by the days supply recorded at the time of pharmacy dispensing, allowing for a gap between dispensings of up to 15 days. This gap is allowed in consideration of plausible delays in obtaining medication refills and continued use beyond the days supplied where medication has been missed due to imperfect adherence, and will be varied in sensitivity analyses (see Section 7.9.2). Codes used to identify study medications are included in Annex 3.1.

The treatment segment ends at the earliest of the following events:

- 1. Fifteen days after the end of the observed days supply for the medication received on the index date without a subsequent dispensing of COPD medication (i.e., discontinuation)
- 2. Initiation of triple therapy (i.e., addition of ICS to Tio+Olo or a LAMA to LABA/ICS (i.e., treatment escalation, applies to Tio+Olo only)
- 3. Any other change in use of study medication by active ingredient, inclusive of a change to a different combination therapy, change from a fixed form to a free form combination therapy, or a change from combination therapy to monotherapy (i.e., switch)

Changes in dose for medications started on the index date will not impact the end of the treatment segment. Codes used to identify study medications are included in Annex 3.1.

7.4.2 **Outcome(s)**

7.4.2.1 **Primary outcome(S)**

The primary outcome event for effectiveness is the first COPD exacerbation to occur after cohort entry. The event is defined as follows:

- Severe exacerbation: •
 - Hospitalization with a principal discharge diagnosis of COPD.
 - Moderate exacerbation:
 - An ED visit with a discharge diagnosis of COPD and/or
 - Dispensing of an antibiotic and an oral corticosteroid on the same day

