Time to the first COPD exacerbation will be measured from cohort entry until the occurrence of a hospitalization for COPD (severe exacerbation) or ED visit for COPD with the prescription of an antibiotic and/or an oral corticosteroid on the same day (moderate exacerbation). Severe and moderate exacerbations will be considered as a composite for main analyses. Sensitivity analyses will stratify by exacerbation severity.

Although there is precedent for defining moderate exacerbation based on use of antibiotics for a respiratory infection without requiring concomitant oral corticosteroids, we have chosen

a more restrictive definition of exacerbation. Because diagnoses listed on outpatient claims often correspond to a patient's past medical history in addition to acute problems, we expect limited ability to capture the indication for which antibiotics are prescribed. As such, including antibiotics alone as a case definition for exacerbation would introduce potentially substantial misclassification of outcome where antibiotics were truly given for non-respiratory infections. Given that our analyses will yield estimates on a ratio measure, non-differentially reduced sensitivity is a less important threat to validity than reduction of outcome specificity, which produces an expectation of bias towards the null hypothesis. In order to test our assumptions that the sensitivity of our outcome definition is not differential between the Tio+Olo and LABA/ICS groups, we would produce counts of patients with antibiotics alone during follow-up, and determine whether the proportion of potential exacerbations that we excluded through this design decision is comparable across groups.

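### On the plan's own premise, comparing antibiotic-only shares between groups cannot show whether outcome sensitivity is non-differential

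*Combined protocol and SAP*

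**What the plan says.** Section 7.4.2.1 sets a narrow moderate-exacerbation definition. Its dispensing route is "Dispensing of an antibiotic and an oral corticosteroid on the same day". Antibiotics alone do not count, for two stated reasons: counting them "would introduce potentially substantial misclassification of outcome where antibiotics were truly given for non-respiratory infections", and "we expect limited ability to capture the indication for which antibiotics are prescribed".

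The narrow definition is defended on the ground that, for a ratio measure, "non-differentially reduced sensitivity is a less important threat to validity than reduction of outcome specificity". The paragraph adds that it is "reduction of outcome specificity, which produces an expectation of bias towards the null hypothesis".

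The assumption that "the sensitivity of our outcome definition is not differential between the Tio+Olo and LABA/ICS groups" is then to be tested: "we would produce counts of patients with antibiotics alone during follow-up, and determine whether the proportion of potential exacerbations that we excluded" is similar by group. No threshold, interval, weighting, person-time basis or reference standard is given for this comparison.

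**The concern.** The dispensings judged too contaminated to count as outcomes become the yardstick for the outcome's sensitivity. Dispensings for other infections do not fall when a treatment prevents exacerbations. The excluded share can therefore move when sensitivity is equal, and stay level when it is not.

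This matters because a difference in sensitivity passes straight into the estimate: the captured-event ratio is roughly the true ratio times the ratio of the two sensitivities. A report could state that sensitivity was shown to be comparable, or was not, from a statistic that supports neither statement.

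**Working it through.** **Inputs.** The plan gives no figure for this check, so there is none to reproduce. HR 0.85 is borrowed from Section 7.7 as an effect size only. Group sizes of 5,458 (Tio+Olo) and 42,361 (LABA/LAMA/ICS) are from the abstract. Sensitivity and antibiotic rates are assumptions, shown over a range.

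**Model.** In each group let L be the true exacerbation rate, s the sensitivity of the narrow definition, and b the rate of antibiotic-only dispensing for anything else. L is 1 in the reference group, so b is in multiples of that rate. Suppose every missed exacerbation appears as an antibiotic-only dispensing, which is the case kindest to the check. Then

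share = ((1 − s)L + b) / (L + b), so 1 − share = sL / (L + b).

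Taking the ratio of the two groups:

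(1 − share₁)/(1 − share₀) = (s₁L₁/s₀L₀) ÷ ((L₁ + b₁)/(L₀ + b₀)).

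That is the narrow-definition rate ratio over the broad-definition rate ratio. Shares match only when these two ratios agree. The plan itself expects false positives to pull the broad ratio towards 1. With equal sensitivity and a real effect, the shares should therefore differ. Each group has three unknowns (L, s, b) and two observed counts, so s is not identified.

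**Results.**

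| Scenario | Reference share | Other share | Captured-event ratio |
|---|---|---|---|
| True HR 0.85, s = 0.60 in both, b = 0.5 | 0.9/1.5 = 60.0% | 0.84/1.35 = 62.2% | 0.85 (correct) |
| True HR 0.85, s = 0.60 vs 0.635, b = 0.5 | 60.0% | 60.0% | 0.90, not 0.85 |
| True HR 0.85, s = 0.60 vs 0.653, b = 1 | 70.0% | 70.0% | 0.925, not 0.85 |
| True HR 1, s = 0.60 in both, b = 0.5 vs 0.625 | 60.0% | 1.025/1.625 = 63.1% | 1.00 (correct) |
| True HR 1, s = 0.60 vs 0.65, b = 0.5 vs 0.625 | 60.0% | 0.975/1.625 = 60.0% | 1.08, not 1.00 |

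Over s = 0.4 to 0.8 and b = 0.25 to 2, with equal sensitivity, the shift is 1.1 to 3.2 points at HR 0.85 and 2.5 to 7.1 points at HR 0.70. With b = 0 the share is exactly 1 − s and the check works. It also works at HR 1 if b is the same in both groups.

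**Second model.** Now let only part of the missed events appear as antibiotic-only: r is the true rate, a the antibiotic-only fraction, s the counted fraction and n the other antibiotic use. Share = (ra + n)/(ra + n + rs). With n = 0.6:

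- Reference (r = 1, a = 0.30, s = 0.50): 0.90/1.40 = 64.3%.
- Equal sensitivity, r = 0.85: 0.855/1.28 = 66.8%.
- No effect, a = 0.35, s = 0.45: 0.95/1.40 = 67.9%.
- r = 1.30, a = 0.35, s = 0.45: 1.055/1.64 = 64.3%, matching the reference although the captured ratio is 1.30 × 0.45/0.50 = 1.17.

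The first three figures are 54.5%, 56.6% and 59.1% at n = 0.3, and 70.6%, 73.1% and 73.5% at n = 0.9. The exact match needs r = 1.58 at n = 0.3 and r = 1.23 at n = 0.9, so it is a particular combination of values.

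**Precision.** Assume 30% to 60% of patients have a potential event and the share is 60%. Then 1.96 × √(0.24/n₁ + 0.24/n₀) is 2.5 to 1.8 points. A 2.2-point artefact would reach two-sided 5% significance 41% to 69% of the time.

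**Follow-up.** The plan counts patients. Take identical rates in both groups (0.9 antibiotic-only and 0.5 counted events per year, independent, anyone with a counted event classed there). Fixed follow-up of 0.5 versus 0.7 years gives 28.2/(28.2 + 22.1) = 56.1% versus 32.9/(32.9 + 29.5) = 52.7%. Follow-up could differ, because Section 7.4.1 ends a treatment segment at escalation for Tio+Olo only.

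**The case against.** The strongest reply is that this is an added count with no decision rule, and that it leaves the HR unchanged. The case for the narrow outcome is the specificity argument, and Sections 7.4.2.1 and 7.9.1 already plan separate analyses of severe and moderate events. Severe events are hospitalizations and do not depend on the antibiotic rule. At HR 0.85 the artefact is small enough that many readers would call the shares comparable. All of this stands. A reader might infer that the primary outcome's validity rests wholly on the check, or that the primary HR is biased; the documents support neither.

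It is also true that an unfiltered broad outcome carries the same information as the share. In the matching case above the narrow ratio is 1.17 and the broad ratio is 1.64/1.40 = 1.17, and both miss 1.30. A broader-outcome HR therefore cannot prove equal sensitivity either. It helps only by adding events the check never sees and by reducing contamination.

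Two further criticisms are weaker than they look. The protocol does not say whether the comparison is crude or weighted, so calling it unweighted goes too far. The LABA/ICS label also appears in Sections 7.3 and 7.9.1, so it is a naming fault across the document and says nothing about the logic of the check.

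What remains is that the protocol says the comparison will test non-differential sensitivity, and on its own premise it cannot.

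**Conclusion.** The point holds in a limited form. Given the protocol's statement that antibiotic-only dispensings include other infections, the excluded share mixes treatment effect, other antibiotic use and sensitivity. Equal use for other reasons cannot be taken for granted either, since pneumonia is a secondary outcome of this comparison. The size is about 1 to 3 points at HR 0.85 under assumed rates, and some combinations of a real effect and unequal sensitivity give matching shares.

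To say that the check can never work would be too strong. It works if other antibiotic use is nil, or if there is no treatment effect and other use is equal. The protocol's own text rules out the first and cannot assume the second.

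**What to change.** - Keep the antibiotic-only counts as description: propensity-weighted, per person-year, by Tio+Olo and LABA/LAMA/ICS. Remove the statement that they test non-differential sensitivity.
- Add a weighted Cox sensitivity analysis with a broader outcome. It would contain the primary definition, oral-corticosteroid-only dispensings, and antibiotic-only dispensings with an acute respiratory diagnosis within a few days. A COPD code alone would add little, because Section 7.3 requires one of every cohort member. Fix the code list and window in advance.
- Report that model as showing whether the HR depends on the restrictive definition, and not as proof of equal sensitivity. Read it beside the planned severe-only analysis.
- Extend the planned quantitative bias analysis, which Section 7.4.3 directs at residual confounding, to a range of group-specific outcome sensitivities.
- Reconcile the two descriptions of a moderate exacerbation in Section 7.4.2.1: the list treats same-day dual dispensing as a route of its own, while the next paragraph ties the drugs to an ED visit. Until then it is unclear which events count as excluded.

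The cost is one code list, one extra model and a wider bias analysis on claims already held. Specificity is lower in that sensitivity analysis only; the primary outcome and model stay as they are.

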7.4.2.2 Secondary outcome(s)

The secondary outcome is the occurrence of the first hospitalization for community-acquired pneumonia (serious pneumonia). Pneumonia will be defined using ICD-9-CM diagnoses 481.x-486.x; 487.0, 507.x, 507.0, 507.1, 507.8, 510.0, 510.9, 511.0, 513.0, 514.x, 517.1, 519.8, 530.84, and ICD-10 diagnosis codes J10.0; J11.0; J12-J18; J22; J69; J85.0; J85.1; J86. This definition has been used successfully in COPD [P07-09514; P16-10095].

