7.7 STUDY SIZE

	Tio	+Olo	ICS/LABA	A/LAMA
	Ν	%	Ν	%
New users	8,233	100.0	82,534	100.0
At least 12 months of				
pre-index eligibility	6,263	76.1	50,153	60.8
Age 40 +	6,126	97.8	48,267	96.2
At least 1 diagnosis of COPD	5,469	89.3	42,227	87.5
At least 1 eosinophil % result				
prior to the index date	2,207	40.4	15,699	37.2
Eosinophil result (N, % of				
those with a result)				
0-2%	1,059	48.0	7,488	47.7
2-4%	745	33.8	5,136	32.7
4%+	403	18.3	3,075	19.6
Eosinophil result, patients				
with low exacerbation				
history(0 inpatient and 0-1				
outpatient events at baseline,				
N, %)				
<300 cells/uL	1,381	30.0	9,516	27.3
\geq 300 cells/uL	481	10.5	3,481	10.0
Unknown	2,739	59.5	21,813	62.7
Eosinophil result, patients				
with high exacerbation history				
(1 + inpatient or 2 + outpatien)				
t events at baseline, N, %)			vents	
<300 cells/uL	226	26.0	1,888	25.5
≥300 cells/uL	105	12.1	707	9.5
Unknown	537	61.9	4,822	65.0

Preliminary patient counts in the HIRD are shown here:

In a recent analysis of the risk of exacerbations based on Clinical Practice Research Datalink (CPRD), a total of 2,000 patients per cohort detected a 15% difference in risk of a first exacerbation (hazard ratio 0.85) with over 90% power. As such, overall analyses and analyses that are stratified based on the presence of claims-based indicators of exacerbation are expected to have adequate power. Analyses limited to individuals with specific eosinophils will be more limited. Given low expected sample size, stratification by eosinophil analysis within individuals with exacerbations at baseline will not be performed by Eosinophil categories.

7.8 **DATA MANAGEMENT**

All statistical analysis for the study will be conducted using SAS version 9.4 or higher (SAS Institute, Cary, NC). All sensitive data pertaining to the study will be stored on secured servers with access only permitted by approved study team members.

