Stratified analyses will use the same approach. Because not all individuals will have available laboratory result data available, fine stratification and reweighting by propensity score will be repeated within the subset of the cohort with available results to create weighted populations suitable for these stratified analyses. Potential effect-modification by B-Eosinophils and/or exacerbation history will be studied by comparing models with and without interaction terms and through qualitative consideration of differences in stratum-specific estimates.

The analysis of the risk of pneumonia will also use a time-dependent Cox proportional hazard regression model with an as-treated approach, similar to that of the primary analysis.

In addition, we will repeat the primary effectiveness analysis on the time to exacerbation separately for moderate and severe exacerbations.

In terms of healthcare utilization, we will present continuous and categorical variables using standard descriptive statistics to describe total visits and total costs related to inpatient, outpatient, office visit, and emergency care as well as total pharmacy dispensings, distinct medications used, and pharmacy costs. Utilization and costs will be stratified to facilitate comparison between Tio+Olo and LABA/ICS, and presented by individual setting and as a composite. All-cause and COPD-specific data will be shown.

Proprietary confidential information © 2019 Boehringer Ingelheim International GmbH or one or more of its affiliated companies

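### The community-acquired pneumonia outcome has no diagnosis-position or present-on-admission rule, and section 7.4.2.2 and Annex 3.2 give conflicting code lists, so pneumonia arising in hospital could be counted

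*Combined protocol and SAP*

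**What the plan says.** Section 7.4.2.2 defines the only secondary outcome: "The secondary outcome is the occurrence of the first hospitalization for community-acquired pneumonia (serious pneumonia". It then gives the codes. For ICD-9: "Pneumonia will be defined using ICD-9-CM diagnoses 481.x-486.x; 487.0, 507.x, 507.0, 507.1, 507.8, 510.0, 510.9, 511.0, 513.0, 514.x, 517.1, 519.8, 530.84". For ICD-10: "ICD-10 diagnosis codes J10.0; J11.0; J12-J18; J22; J69; J85.0; J85.1; J86". It adds that the definition has been used in COPD before, with two citations. It does not refer to Annex 3.2.

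Annex 3.2 (definitions of study outcomes) prints its own pneumonia list, without code labels. That list includes 997.31, J95.4 and J95.89.

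For the primary outcome, section 7.4.2.1 does fix the diagnosis position. A severe exacerbation is a "Hospitalization with a principal discharge diagnosis of COPD". The same section explains why a restrictive exacerbation definition was chosen. For a ratio estimate, the authors regard lost sensitivity as a lesser threat than "reduction of outcome specificity, which produces an expectation of bias towards the null hypothesis".

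On analysis, section 7.9.1 says: "The analysis of the risk of pneumonia will also use a time-dependent Cox proportional hazard regression model with an as-treated approach". It adds no outcome rule and no sensitivity analysis of the pneumonia definition.

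**The concern.** As the plan is written, only its name makes the outcome community-acquired. Two programmers working from it could build different endpoints, because they would have to choose the code list and the diagnosis positions themselves.

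The more inclusive choices would let in pneumonia that began in hospital, including during a COPD admission. Exacerbation and pneumonia are the two time-to-event outcomes on which an ICS-free and an ICS-containing regimen are compared. An exacerbation is not among the events that end follow-up in sections 7.3 and 7.4.1. A single stay, with COPD as principal diagnosis and pneumonia in a secondary position, could therefore enter both analyses. The pneumonia estimate would then partly reflect COPD admissions.

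**Working it through.** The plan gives no event count, rate or power for pneumonia, so there is no figure to reproduce. The power statement in section 7.7 ("a total of 2,000 patients per cohort detected a 15% difference in risk of a first exacerbation (hazard ratio 0.85) with over 90% power") concerns exacerbation and does not bear on this point.

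**Step 1: look for a rule.** The objectives (6), subjects (7.3), exposure and outcome definitions (7.4), bias (7.6), analysis (7.9.1), limitations (7.11) and Annex 3.2 contain no diagnosis-position, present-on-admission or days-from-admission rule for pneumonia. Annex 3.4 is in the table of contents, but its text was not available to me.

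**Step 2: compare the two code lists.** Annex 3.2 prints 36 ICD-9 and 34 ICD-10 pneumonia entries.

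| | ICD-9 | ICD-10 |
|---|---|---|
| In Annex 3.2, not in 7.4.2.2 | 480, 480.1, 480.2, 480.3, 480.8, 480.9, 997.31 | J95.4, J95.89 |
| In 7.4.2.2, not in Annex 3.2 | 487.0, 507.x, 510.0, 510.9, 511.0, 513.0, 514.x, 517.1, 519.8, 530.84 | J22, J85.0, J86 |

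So 7 of the 36 ICD-9 entries and 2 of the 34 ICD-10 entries in the annex fall outside 7.4.2.2. Under J69, the annex has only J69.0. Neither list is a subset of the other.

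**Step 3: read the disputed codes.** In the standard classification, 997.31 is ventilator-associated pneumonia, J95.4 is chemical pneumonitis due to anaesthesia, and J95.89 is other post-procedural respiratory complications. None of these fits the outcome's name. Section 7.5 says diagnoses are in ICD-10 from October 2015, so 997.31 can matter only in the earlier part of the 2013 to 2019 window.

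**Step 4: see what each choice lets in.**
- 7.4.2.2 list, principal position: the three codes are out, and a COPD-principal stay is not a pneumonia event.
- 7.4.2.2 list, any position: the three codes are out, but an ordinary pneumonia code such as 486 or J18.9 in a secondary position still qualifies, whenever the pneumonia began.
- Annex list, either position: the three codes are eligible.

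The position rule is therefore the main gap. Deleting three codes would not close it.

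**Step 5: illustrate the size (every input is assumed).** Let f be the share of counted Tio+Olo pneumonia events that are not community-acquired. Let HR be the true community-acquired hazard ratio (triple versus Tio+Olo) and HRc the ratio for the other events. The component hazards add, so with f constant over time:

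HR observed = (1 − f) × HR + f × HRc

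| f | HR 1.5, HRc 1 | HR 1.2, HRc 1 | HR 1.5, HRc 0.85 |
|---|---|---|---|
| 5% | 1.475 | 1.19 | 1.4675 |
| 10% | 1.45 | 1.18 | 1.435 |
| 20% | 1.40 | 1.16 | 1.370 |
| 30% | 1.35 | 1.14 | 1.305 |

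For example, 0.90 × 1.5 + 0.10 × 1 = 1.45. The estimate moves towards HRc, whatever HRc is. If HRc equals HR, nothing changes. If HRc exceeds HR, the observed value rises.

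**The case against.** The strongest reply is that the wording already implies a principal diagnosis. In section 7.4.2.1 the paragraph on time to first exacerbation uses the phrase hospitalization for COPD as shorthand for the principal-diagnosis rule just above it. Read the same way, hospitalization for pneumonia would exclude a COPD-principal stay. That reading is plausible, so such stays can only be said to be possibly counted. It is not stated, though, and the position is spelled out for COPD but not for pneumonia.

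Second, the three codes are absent from the list in 7.4.2.2 itself, and nothing says that the annex overrides it. This is correct, and it limits the point to a conflict between lists. The conflict is itself a defect.

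Third, the definition is said to rest on two published studies. Their position rule cannot be checked from the documents. The statement follows the 7.4.2.2 list and does not explain the different annex list.

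Fourth, diagnosis position is an imperfect filter. Pneumonia already present at admission but coded after COPD is truly community-acquired, and a principal-only rule loses it. This stands, and it is why the any-position definition should be kept as a sensitivity analysis. It also means that the share of pneumonia events coded second to COPD would overstate f.

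Fifth, one stay contributing to two separately modelled outcomes is not an error in itself. That also stands. What is missing is a count of how often it happens.

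**Conclusion.** The point holds as a gap in specification and a conflict between code lists. Section 7.4.2.2 does not make the outcome community-acquired in operation, and Annex 3.2 contradicts its code list, including with three codes that do not fit the outcome's name. By the authors' own argument in 7.4.2.1, loss of specificity is the greater threat to a ratio estimate, and here they leave it open.

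A reader might infer more: that the outcome definitely includes ventilator-associated pneumonia, that COPD stays with secondary pneumonia will be counted twice, and that a real pneumonia difference will be understated. The documents do not support this. The codes stand in only one of two competing lists, and the diagnosis position is unspecified. The direction of bias depends on the hazard ratio of the misclassified events, which the documents do not give. Understatement of a raised hazard ratio follows only if that ratio lies below the true pneumonia ratio.

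The figures in the working are illustrations and not bounds. The reading of the three codes rests on the standard classification, since the annex prints no labels. The issue should be corrected, but it affects the secondary outcome and not the primary one.

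**What to change.** - Reconcile 7.4.2.2 and Annex 3.2 into one pneumonia code list, and have 7.4.2.2 refer to it.
- Remove 997.31, J95.4 and J95.89 from the outcome set.
- State in 7.4.2.2 that the main analysis requires a principal discharge diagnosis of pneumonia, matching the COPD hospitalization rule. Add the any-position definition as a sensitivity analysis.
- Report, by treatment group, how many stays count for both exacerbation and pneumonia.

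The work is a wording change, one code list, one extra model run and one count on existing data. The price is fewer pneumonia events and a wider interval in the main analysis. Stays with pneumonia coded second, for example after sepsis, respiratory failure or COPD, would appear only in the sensitivity analysis.
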